5.6 Study Drug Discontinuation

Subjects should be discontinued from study drug treatment in the following situations:

- A female subject desires to become pregnant at the current time, stops contraception or expels her intrauterine device/implant, or becomes pregnant
- A female subject has new breast findings (e.g. a palpable mass or abnormal mammography, discharge), or has abnormal vaginal discharge or bleeding
- The subject decides to discontinue study drug treatment, or withdraws consent from the study
- The subject receives a strong CYP3A4 inhibitor (See [Appendix B](#))
- Any medical condition that may jeopardize the subject's safety if study drug is continued, in the investigator's and/or Sponsor's opinion; this may include the development of persistently (2 successive occasions) abnormal thyroid function tests (TSH >10, or TSH > 6 with low free T4; TSH <0.1, or TSH < 0.35 with high free T4); abnormal morning prolactin, cortisol, or corticotropin levels; or signs and symptoms of adrenal insufficiency

- Discontinuation is deemed to be in the best interest of the subject, in the investigator's and/or Sponsor's opinion, including evidence that the subject does not meet inclusion/exclusion criteria intended primarily for safety reasons, or a persistent lack of adherence to study procedures

The Sponsor or designee should be contacted within 24 hours of investigator's awareness of any study drug treatment discontinuation. Investigators should make every effort to contact the Sponsor or designee before discontinuing study drug treatment, if possible.

Subjects who discontinue treatment with study drug prior to completing the treatment period will enter a 5-week follow-up (post-study drug observation) period following the last dose of study drug (see [Section 3.1](#), [Section 6.5.10](#)). Every effort should be made for subjects to complete the 5-week observation period and the Follow-up visit after a subject has discontinued from study drug.

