- Perform targeted physical examination, including weight
- Assess and record any AEs and SAEs
- Collect returned study drug
- Utilize IWRS to assign new bottle of study drug
- Review eDiary for compliance, re-train subject as needed
- Confirm next scheduled visit

6.5.9 *Week 10 Visit*

The Week 10 visit occurs 70 days (\pm 7 days) after the Baseline visit. At the Week 10 visit, the following procedures and assessments are to be performed:

- Ask the subject to complete the DLQI, HADS, and ESS questionnaires
- Assess and record any changes in the subject's concomitant medications
- Female subjects should be queried for presence of new breast masses or abnormal discharge, and abnormal vaginal bleeding or discharge
- Review menstrual diary and record dates of menstrual flow (if applicable)

- Obtain ECG
- Obtain vital signs
- Perform targeted physical examination, including weight
- Perform IGA PN-A
- Perform IGA PN-S
- Perform a urine pregnancy test for females of childbearing potential (with positive or equivocal results confirmed by a serum pregnancy test)
- Draw blood for clinical laboratory tests (morning blood sampling due to Endocrine assessments)
 - Reproductive endocrine labs for females under 55 years of age at consent
 - Endocrine
 - Hematology
 - Chemistry
- Collect PK blood sample
- Assess and record any AEs and SAEs
- Collect returned study drug
- Obtain photos (at selected sites, only subjects that signed photography consent)
- Review eDiary for compliance, inform subject to continue entering WI-NRS score until Follow-up visit
- Review study drug compliance with re-training as required
- Confirm next scheduled visit date

6.5.10 ***Post-Drug Observation Visits***

There are five (5) post-drug observation visits, and a Follow-up visit to complete the post-observation period.

The Post-Drug Observation Visits occur 3 days (± 1 days), 7 days (± 3 days), 14 days (± 3 days), 21 days (± 3 days), and 28 days (± 3 days) after the Week 10 Visit.

At the Post-Drug Observation Visits, the following procedures and assessments are to be performed:

- Ask the subject to complete the HADS and ESS questionnaires
- Assess and record any changes in the subject's concomitant medications
- Female subjects should be queried for presence of new breast masses or abnormal discharge, and abnormal vaginal bleeding or discharge
- Review menstrual diary and record dates of menstrual flow (if applicable)
- Obtain vital signs
- Assess and record any AEs and SAEs

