APPENDIX A SCHEDULE OF ACTIVITIES AND ASSESSMENTS

Table 2 Schedule of Visit Activities

Examination	Screening	Mid-Screening ^{TC}	Baseline ¹	Week 1 (± 3 days) ^{TC}	Week 2 (± 3 days)	Week 4 (± 3 days)	Week 6 (± 3 days)	Week 10 (± 7 days)	Post-drug obs.: 3 days (±1 day), and 7, 14, 21, & 28 days (±3 days) after Week 10 ²	Follow-up: 35 days (+3 days) after Week 10 ²	Early Treatment Discontinuation
Demographics	X										
Informed consent	X										
WI-NRS ³	X	X	X	X	X	X	X	X	X	X	X
DLQI			X			X		X			X
HADS, ESS			X			X		X	X	X	X
ECG	X				X	X		X		X	X
Vital signs	X		X		X	X	X	X	X	X	X
Medical history (and prior medications)	X	X	X								
Physical exam ⁴	X		X		X	X	X	X		X	X
Concomitant medications			X	X	X	X	X	X	X	X	X
Labs ⁵	X				X			X		X	X
Urine pregnancy test ⁶	X		X			X	X	X		X	X
PK blood draw					X	X		X			
Review of I/E criteria	X	X	X								
IGA PN-A and IGA PN-S			X		X	X		X		X	X
Photography (selected sites)			X					X		X	X
Dispense/review menstrual diary (if applicable)	X		X		X	X	X	X	X	X	X
Dispense/collect eDiary	X									X	X
eDiary review/compliance ⁷		X	X	X	X	X	X	X		X	
Dispense and/or collect study drug			X		X	X	X	X			X
Review study drug compliance					X	X	X	X			
AEs/SAEs ⁸	X	X	X	X	X	X	X	X	X	X	X

^{TC}Telephone Contact: The Mid-Screening telephone contact should only occur for subjects who require a washout longer than 2 weeks, at least 15 days prior to the scheduled Baseline visit.

¹All visits and windows should be scheduled based on the Baseline Visit (Day 1)

²The Post-Drug observation period visits occur 3 days (±1 day), and 7, 14, 21, and 28 days (±3 days), and the Follow-up visit occurs 35 days (+3 days) after the Week 10 visit or the last dose of study drug for subjects who discontinue study drug early.

³WI-NRS at Screening visit will be collected manually on paper for Inclusion/Exclusion criteria. All subsequent WI-NRS are collected daily via eDiary.

⁴Screening physical exam is complete and includes height and weight; other physical exams are targeted and include weight.

⁵Labs are ideally performed in the morning, particularly at visits with endocrine assessments (including Reproductive Endocrinology for females under 55 at age of consent) at Screening, Week 10 and Follow Up. Iron Studies, serum IgE and Serology labs are done only at Screening visit; endomysial antibody test and other optional studies only performed at Screening;

⁶Female subjects of childbearing potential only. Serum pregnancy test is required for positive or equivocal results

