⁷See Table 3 for eDiary assessments

⁸During the period between informed consent and first study drug dose, only SAEs caused by a protocol-mandated intervention will be collected.

Table 3 Schedule of eDiary Assessments

An eDiary device is provided to subjects at the Screening visit and collected at the Follow-up visit.

Device	Assessment	Frequency and Duration of Assessment
eDiary	WI-NRS	Once daily from Screening/Mid-Screening visit through the Follow-up visit
eDiary	Dosing	Once daily from Baseline visit through Week 10 visit or study drug discontinuation

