### 6.1.3 Visit Windowing

[figure not shown]
Data will be summarized based on nominal visit indications. Due to protocol revisions, differing follow-up visit schedules were used. Data collected during post-treatment follow-up will be summarized as

Protocol Version(s)	Nominal Visit	Analysis Visit
V2.0; V2.1	3-Week Follow-up	3-Week Follow-up
V2.0; V2.1	5-Week Follow-up	5-Week Follow-up

V3.0	Post-Drug Observation Day 3	3-Day Follow-up
V3.0	Post-Drug Observation Day 7	1-Week Follow-up
V3.0	Post-Drug Observation Day 14	2-Week Follow-up
V3.0	Post-Drug Observation Day 21	3-Week Follow-up
V3.0	Post-Drug Observation Day 28	4-Week Follow-up
V3.0	Post-Drug Observation Day 35	5-Week Follow-up

In addition, a "Latest Follow-up" visit will be summarized, which will include the latest available follow-up information for each subject from the 3-, 4-, 5- Week Follow-up visits.

Information collected at early treatment discontinuation visits will be mapped to the most appropriate visit based on the midpoints between scheduled visits.

For example, if a subject terminates use of study drug on or after Day 22 but before Day 36, data collected at the early end of treatment visit will be mapped to the Week 4 evaluation for summaries. If the subject has Week 4 values present, the data collected at the early end of treatment visit will not replace the data collected at Week 4. For the sensitivity efficacy analyses, last observation carried forward (LOCF) will be applied subsequent to mapping the information to the appropriate visit.

Additionally, WI-NRS will be summarized at Weeks 1, 2, 3, 4, 5, 6, 7, 8, 9, 10 and 3- and 5-Week Follow-up by averaging the daily results for the 7 days prior to each week. The weekly average values will be calculated if a subject has at least four responses during the 7 day range, as defined below:

Week/Visit	Study Day Range
Week 1	2-7 (as Day 1 may be pre or post first dose)
Week 2	8-14
Week 3	15-21
Week 4	22-28
Week 5	29-35
Week 6	36-42

Week 7	43-49
Week 8	50-56
Week 9	57-63
Week 10	64-70
3-Week Follow-up	Post-treatment days 15-21
5-Week Follow-up	Post-treatment days 29-35

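### After an early drug stop, no diary check or reminder is listed while the Week 10 score is being recorded, and Table 2 appears to take the diary back

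*Protocol*

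**What the plan says.** **Path after an early stop.** Under Protocol 5.6 the subject "will enter a 5-week follow-up (post-study drug observation) period following the last dose of study drug". Table 2, footnote 2, places Follow-up "35 days (+3 days) after the Week 10 visit or the last dose of study drug for subjects who discontinue study drug early" and times the five post-drug visits (Days 3, 7, 14, 21, 28) in the same way. The text of 6.5.10 counts those five visits from the Week 10 visit only.

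**Diary review.** Section 6.5.10 introduces its list with "At the Post-Drug Observation Visits, the following procedures and assessments are to be performed". The items are HADS and ESS, concomitant medication, a query to female subjects, the menstrual diary, vital signs and adverse events. The Table 2 row "eDiary review/compliance" is marked at Mid-Screening, Baseline, Weeks 1, 2, 4, 6 and 10, and Follow-up. It is blank at the post-drug visits and at Early Treatment Discontinuation, a visit for which the protocol has no procedure list.

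**Duty to record.** Table 3 requires WI-NRS "Once daily from Screening/Mid-Screening visit through the Follow-up visit", and 6.1.1 says the same. The only visit-level reminder is at the Week 10 visit (6.5.9): "Review eDiary for compliance, inform subject to continue entering WI-NRS score until Follow-up visit".

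**Device.** The Table 2 row "Dispense/collect eDiary" is marked at Screening, Follow-up and Early Treatment Discontinuation. Table 3 and 6.5.11 have the device collected at Follow-up.

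**Use of the data.** SAP 6.1.3 sets Week 10 as Days 64-70: "The weekly average values will be calculated if a subject has at least four responses during the 7 day range". Under SAP 6.1.5, diary data are set to missing only after excluded therapy for worsening. Other entries made after a drug stop are kept, and a week with fewer than 4 entries is imputed.

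**The concern.** The plan wants post-stop diary data: the WI-NRS row of Table 2 is marked at Early Treatment Discontinuation and at the post-drug visits, and the analysis uses those entries. But the visit schedule lists no check of them and no reminder, and one cell of the same table appears to take the device away.

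At stake is the observed primary outcome in subjects who leave treatment. When it is missing and no non-responder rule applies, responder status comes from the multiple imputation in Protocol 8.2 and SAP 6.1.5. That model is fitted within arm on baseline and weekly scores and has no term for having stopped drug. A stopper's missing Week 10 is therefore modelled like that of subjects with similar scores who stayed on drug. The lost value may be avoidable, since the subject is seen up to six times before Follow-up.

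**Working it through.** The plan gives no figure on this point. Its power statement rests on redacted rates and does not enter. The check is a day count.

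**Inputs.** Last dose on study Day L; Follow-up on Day L+35 to L+38 (Table 2, footnote 2); diary through Follow-up (Table 3); window Days 64-70 with at least 4 entries (SAP 6.1.3).

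**Lower limit.** Let E be the last diary day. The entries possible in the window are min(70, E) - 63, or zero if that is negative. Four entries need E of at least 67; seven need E of at least 70.

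| Follow-up at | Visit-day entry | E | 4 possible from | 7 possible from |
|---|---|---|---|---|
| L+35 | counted | L+35 | Day 32 | Day 35 |
| L+35 | not counted | L+34 | Day 33 | Day 36 |
| L+38 | counted | L+38 | Day 29 | Day 32 |
| L+38 | not counted | L+37 | Day 30 | Day 33 |

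For a last dose before Day 29-33, Week 10 is always missing, whatever the site does.

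**Upper limit.** Entries in the window up to the last dose number L - 63. Four need L of at least 67, so post-stop entries are needed up to L = 66. The whole window falls after the stop for L from Day 32-36 to Day 63.

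**Length of the gap.** From last dose to the next listed review is 35-38 days. The longest nominal on-drug interval is Week 6 to Week 10: 70 - 42 = 28 days.

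**Example, last dose Day 40.** Post-drug visits fall near Days 43, 47, 54, 61 and 68, with Follow-up at Day 75-78. The Day 61 visit is three days before the window opens and the Day 68 visit is inside it; neither lists a diary check. The last listed review was Week 4 (28 days after Baseline, so Day 29), which makes 75 - 29 = 46 days between reviews.

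**Chance of a usable week.** With independent days at completion rate p (assumed), P(at least 4 of 7) is the sum over k = 4 to 7 of C(7,k) p^k (1-p)^(7-k):

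| p | P(at least 4 of 7) |
|---|---|
| 0.85 | 98.8% |
| 0.70 (entry threshold, inclusion criterion 8) | 87.4% |
| 0.60 | 71.0% |
| 0.50 | 50.0% |

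**Scale, illustration only.** TCP-102 had 9 adverse-event discontinuations in 128 subjects (Protocol 1.5.3). Applied to 280: 280 x 9/128 = 19.7. If all fell in the vulnerable range, expected lost scores would be 19.7 x (1 - 0.988) = 0.2, 19.7 x (1 - 0.874) = 2.5 and 19.7 x (1 - 0.710) = 5.7 at 85%, 70% and 60% completion. If the device is collected at the stop, nearly all 19.7 would be lost.

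**The case against.** **The duty to record is stated repeatedly.** This stands. Section 6.1.1, Table 3, inclusion criterion 8 and the opening of 6.5 all require daily entry for the whole study. A reader might infer that early stoppers are never told to continue; the documents do not support that. What is missing is the check and the reminder at the visits these subjects attend.

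**Section 5.9 already has the diary reviewed at each study visit.** That review serves dosing compliance, and Table 3 ends dosing entries at drug discontinuation, so it does not close the gap.

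**Completers also have an unreviewed window.** Largely true: nothing is listed between Weeks 6 and 10. With both visit windows at their limits that interval could reach 28 + 3 + 7 = 38 days. The contrast is one of degree, but completers are still attending on-drug visits and recording doses daily.

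**Nothing shows that review raises completion.** Correct. The binomial figures show sensitivity to completion, not the benefit of a check.

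**Imputation uses each subject's own scores.** Also correct, including any post-stop weeks recorded. A reader might infer that lost values pull stoppers toward on-drug response and favor serlopitant. That is possible, but neither direction nor size follows from the documents.

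**Manuals may cover it.** Study-specific manuals and the Monitoring and Data Management Plans are not available here. They could add a check, but the conflict over collection lies within the protocol itself.

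**Conclusion.** The point holds for a defined subset: last dose from about Day 29-33 to Day 66, with responder status not already fixed by the lack-of-efficacy or excluded-therapy rules. For them an observed Week 10 score needs post-stop entries that no listed contact checks or prompts for 35-38 days after the last dose.

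The conflict over collecting the device is the more serious part. If sites follow Table 2, the subset has almost no observed Week 10 scores, and review lines alone would achieve nothing.

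It would be wrong to extend this to every early stopper. Before Day 29-33 the diary ends too soon to yield 4 entries in the window; for a last dose on Days 67-69, enough entries can be made before the stop. Effects on power or bias cannot be quantified: the documents give no early-stop rate and the design response rates are redacted. The day range assumes Follow-up within its stated window and a diary kept until then.

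**What to change.** 1. Reconcile Table 2 with Table 3 and 6.5.11. A subject who continues into post-drug observation keeps the eDiary until Follow-up; it is collected at Early Treatment Discontinuation only if the subject is leaving the study.
2. At Early Treatment Discontinuation and at each 6.5.10 visit, add an item to check eDiary completion, retrain if needed, and remind the subject to keep entering WI-NRS until Follow-up. Mark the two blank cells in the Table 2 diary-review row. Because the early-stop visit has no procedure list, give it a short one.

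The longest scheduled stretch after a stop without review falls from 35-38 days to about 7 nominal days. The cost is protocol wording and a few minutes at visits already scheduled; no visit is added and the analysis is unchanged. It does not recover Week 10 for stops before about Day 29-33.

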7 ASSESSMENT OF SAFETY

7.1 Definitions

7.1.1 *Adverse Event*

An AE is any untoward medical occurrence associated with the use of a drug in humans, whether or not considered drug related. An AE can be any unfavorable and unintended sign (e.g. an abnormal laboratory finding), symptom, or disease temporally associated with the use of a drug, without any judgment about causality.

AEs include treatment emergent exacerbations of pre-existing illnesses and AEs that occur as a result of protocol-mandated interventions.

7.1.2 *Serious Adverse Event*

An AE is considered “serious” if it results in any of the following outcomes:

- Death
- Life-threatening AE (i.e. the subject was at immediate risk of death from the event as it occurred. An event that might have led to death if it had occurred with greater severity is not “life-threatening”)
- Inpatient hospitalization or prolongation of existing hospitalization

- Persistent or significant incapacity or substantial disruption of the ability to conduct normal life functions
- Congenital anomaly/ birth defect
- Important medical event (i.e. an event that may not result in death, be life-threatening, or require hospitalization, but which may be considered serious by the investigator or Sponsor, as it may jeopardize the subject and may require medical/surgical intervention to prevent one of the outcomes listed above). Examples of such medical events include allergic bronchospasm requiring intensive treatment in an emergency room or at home, blood dyscrasias or convulsions that do not result in inpatient hospitalization, or the development of drug dependency or drug abuse.

The following are not considered SAEs: a visit to the emergency room or other hospital department < 24 hours that does not result in admission (unless considered an important medical or life-threatening event), an elective surgery planned prior to signing consent, admission as per protocol for planned medical/surgical procedure, and/or routine health assessments requiring admission for baseline/trending of health status (e.g. routine colonoscopy).

The terms “severe” and “serious” are not synonymous. Severity refers to the intensity of an AE (e.g. mild, moderate, or severe pain); the event itself may be of minor medical significance (e.g. severe back pain). “Serious” is a regulatory definition, as defined above. Seriousness (not severity) serves as the basis for defining regulatory reporting obligations.

Severity and seriousness should be independently assessed when recording AEs and SAEs on the eCRF.

7.1.3 *Abnormal Physical Exam, Laboratory, Vital Sign, and Electrocardiogram Findings*

Abnormal physical exam findings that are clinically significant and are identified prior to the first dose of study drug should be recorded as medical history. New or worsening clinically significant abnormal physical exam findings identified after the first dose of study drug should be recorded as AEs.

Only abnormal laboratory, vital sign, and ECG findings that are considered clinically significant by the investigator (e.g. require active management or are associated with accompanying symptoms/signs) will be recorded as medical history or AEs on the eCRF. Abnormal laboratory, vital sign, and ECG findings that occur prior to the first dose of study drug should be recorded as medical history, and abnormal findings that occur after the first dose of study drug should be recorded as AEs.

If the clinically significant laboratory, vital sign, or ECG abnormality is a sign associated with a confirmed disease or condition (e.g. elevated creatinine in a subject diagnosed with

chronic kidney disease), only the diagnosis (chronic kidney disease) needs to be recorded on the AE eCRF (rather than listing individual test findings as AEs).

Separate instances of the same clinically significant laboratory, vital sign, or ECG abnormality across visits should not be recorded as separate AEs or SAEs.

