Any pregnancy occurring in a female subject or the female partner of a male subject, from the first study drug administration through the required follow-up visit must be reported within 24 hours of the investigator's awareness of the pregnancy. See Safety Form Completion Instructions for complete instructions.

The investigator will follow the pregnancy to delivery or other pregnancy outcome.

Pregnancy in a female clinical trial subject or female partner of a male clinical trial subject is not an SAE per se. Complications of such pregnancies (for example, spontaneous abortion) may qualify as SAEs and should be reported as such even if they occur after the Follow-up visit. Any congenital anomalies/birth defects must be recorded and reported as SAEs. See Safety Form Completion Instructions for complete instructions.

7.1.6 *Worsening of Pruritus or PN*

Pruritus or PN should be recorded as an AE or SAE only if considered by the investigator to have worsened in severity beyond the subject's typical fluctuations. It is important to include a description of the nature of the unexpected worsening when recording the AE or SAE (e.g. new PN lesions in previously uninvolved skin).

7.2 **Methods and Timing for Recording and Reporting Adverse Events**

7.2.1 *Adverse Event Reporting Period*

Any AE occurrence during the study must be recorded on source documentation and eCRF at the site, in accordance with protocol instructions.

AEs and SAEs will be recorded from the first study drug administration through the follow-up visit. After the required follow-up visit, only SAEs that are believed to be drug-related should be reported.

After informed consent, but prior to initiation of study drug, only SAEs considered by the investigator to be caused by a protocol-mandated intervention will be collected (e.g. SAEs related to invasive procedures such as blood collection). These procedure-related SAEs should only be reported on the source documents and SAE form, not on the AE eCRF. Subjects who undergo screening procedures but are not randomized into the study will not have SAEs recorded in the clinical database.

7.2.2 *Eliciting Adverse Events*

Investigators will seek information on AEs and SAEs at each subject contact through the follow-up visit. All AEs and SAEs, whether reported by the subject or noted by authorized study personnel, will be recorded in the subject's medical record and on the AE eCRF page,

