7.2.3 Assessment of Severity

All AEs entered into the eCRF will be graded for severity using the National Cancer Institute Common Terminology Criteria for Adverse Events (NCI CTCAE) v4.03 (“[Common Terminology Criteria for Adverse Events \(CTCAE\)](#)” 2010) to describe the maximum intensity of the adverse event.

If the AE cannot be found in the event-specific NCI CTCAE grading criteria, the investigator should use the definitions for Grade 1, 2, 3, and 4 in [Table 1](#).

Table 1 Adverse Event Grading

Grade	Severity	Alternate Description ^a
1	Mild (apply event-specific NCI CTCAE grading criteria)	Asymptomatic or mild symptoms; clinical or diagnostic observations only; intervention not indicated.
2	Moderate (apply event-specific NCI CTCAE grading criteria)	Minimal, local or noninvasive intervention indicated; limiting age-appropriate instrumental activities of daily living (ADL ^b)
3	Severe (apply event-specific NCI CTCAE grading criteria)	Severe or medically significant but not immediately life-threatening; hospitalization or prolongation of hospitalization indicated; disabling; limiting self care ADL ^c
4	Very severe, life threatening, or disabling (apply event-specific NCI CTCAE grading criteria)	Life-threatening consequences; urgent intervention indicated.
5	Death related to AE	

^a Use these alternative definitions for Grade 1, 2, 3, and 4 events when the observed or reported AE is not in the NCI CTCAE listing. A semi-colon indicates ‘or’ within the alternate description of the grade.

^b Instrumental ADL refer to preparing meals, shopping for groceries or clothes, using the telephone, managing money, etc.

^c Self care ADL refer to bathing, dressing and undressing, feeding self, using the toilet, taking medications, and not bedridden.

Source: National Cancer Institute Common Terminology Criteria for Adverse Events (NCI CTCAE) v4.03

Note that severity, a measure of intensity, is not equivalent to seriousness, a regulatory definition of outcome. Regardless of severity, some AEs may meet the criteria for seriousness. See [Section 7.1.2](#) for the definition of an SAE.

If an adverse event changes in severity during the same study period (e.g., treatment period), only the highest severity grade will be recorded on the eCRF.

7.2.4 *Assessment of Causality*

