7.3 Follow-up of Adverse Events and Serious Adverse Events

The investigator must make every effort to follow all AEs and SAEs regardless of attribution until judged resolved or stabilized, the subject is lost to follow-up, or it has been determined that study drug treatment or participation in the study is not the cause of the AE or SAE.

7.4 Reporting Serious Adverse Events to the Sponsor and Institutional Review Board or Ethics Committee

The Sponsor or designee is under obligation to report certain SAEs to regulatory authorities related to investigational drugs in clinical trials. The Sponsor or designee must be notified within 24 hours of an AE when the investigator determines that an AE meets the protocol definition of an SAE, regardless of the cause or relationship to study drug.

An SAE related to study participation occurring before study drug administration and after informed consent should be promptly reported to the Sponsor. If the investigator learns of any SAE at any time after a participant has been discharged from the study, and the SAE is considered likely related to study drug, the SAE should be promptly reported to the Sponsor.

Please see the Safety Form Report Completion Instructions for safety reporting instructions.

The investigator must also comply with applicable requirements concerning reporting of SAEs to the IRB or Ethics Committee (EC). This may include initial or follow-up notification of an SAE or other safety information.

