Preferred Term	Likely Related	xx ( xx.x%)	xx ( xx.x%)
	Likely Unrelated	xx ( xx.x%)	xx ( xx.x%)
Preferred Term	Likely Related	xx ( xx.x%)	xx ( xx.x%)
	Likely Unrelated	xx ( xx.x%)	xx ( xx.x%)

<sup>a Counts reflect numbers of subjects reporting one or more TEAEs that map to MedDRA. At each level of summarization (System Organ Class or Preferred Term) subjects are counted once under the greatest reported relationship.

Note: TEAEs are AEs with an onset after first dose of study drug.

MedDRA Version 21.1.

Table 14.3.1.2.1.1: Overall Summary of Post-Drug Adverse Event (AEs) (Safety Population)

		Placebo			Serlopitant 5 mg	
	Males	Females	Overall	Males	Females	Overall
	(N=xxx)	(N=xxx)	(N=xxx)	(N=xxx)	(N=xxx)	(N=xxx)
Subjects with any Post-Drug AE	xx ( xx.x%)	xx ( xx.x%)				
Number of Post-Drug AEs	XX	XX	XX	XX	XX	XX
Subjects with any Related Post-Drug AE	xx ( xx.x%)	xx ( xx.x%)				
Number of Related Post-Drug AEs	XX	XX	XX	XX	XX	XX
Subjects with any Serious Post-Drug AE	xx ( xx.x%)	xx ( xx.x%)				
Number of Serious Post-Drug AEs	XX	XX	xx	xx	XX	XX
Subjects with any Related Serious Post-Drug AE	xx ( xx.x%)	xx ( xx.x%)				
Number of Related Serious Post-Drug AEs	XX	xx	xx	xx	xx	XX
Subjects who Died	xx ( xx.x%)	xx ( xx.x%)				
Maximum Severity by Subject						
Grade 5	xx ( xx.x%)	xx ( xx.x%)				
Grade 4	xx ( xx.x%)	xx ( xx.x%)				
Grade 3	xx ( xx.x%)	xx ( xx.x%)				
Grade 2	xx ( xx.x%)	xx ( xx.x%)				
Grade 1	xx ( xx.x%)	xx ( xx.x%)				
Maximum Relationship by Subject						
Likely Related	xx ( xx.x%)	xx ( xx.x%)				
Likely Unrelated	xx ( xx.x%)	xx ( xx.x%)				

Note: Table includes AEs with an onset after last dose of study drug.

Table 14.3.1.2.1.2: Overall Summary of Post-Drug Adverse Events (AEs) Occurring 1-7 Days Post Last Dose (Safety Population)

	Placebo	Serlopitant 5 mg
	(N=xxx)	(N=xxx)
Subjects with any Post-Drug AE	xx ( xx.x%)	xx (xx.x%)
Number of Post-Drug AEs	XX	XX
Subjects with any Related Post-Drug AE	xx ( xx.x%)	xx ( xx.x%)
Number of Related Post-Drug AEs	XX	XX
Subjects with any Serious Post-Drug AE	xx ( xx.x%)	xx ( xx.x%)
Number of Serious Post-Drug AEs	xx	XX
Subjects with any Related Serious Post-Drug AE	xx ( xx.x%)	xx ( xx.x%)
Number of Related Serious Post-Drug AEs	XX	XX
Subjects who Died	xx ( xx.x%)	xx ( xx.x%)
Maximum Severity by Subject		
Grade 5	xx ( xx.x%)	xx (xx.x%)
Grade 4	xx ( xx.x%)	xx ( xx.x%)
Grade 3	xx ( xx.x%)	xx ( xx.x%)
Grade 2	xx ( xx.x%)	xx (xx.x%)
Grade 1	xx ( xx.x%)	xx ( xx.x%)

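### Protocol 7.1.3 does not separate a persisting abnormality from one that resolves and recurs, so a recurrence after the last dose is left out of the post-drug AE tables (minor, mainly vital signs)

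*Protocol*

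**What the plan says.** Protocol 7.1.3 sets the recording rules for laboratory, vital sign and ECG findings. Clinically significant "abnormal findings that occur after the first dose of study drug should be recorded as AEs". Where the finding is a sign of a confirmed disease, the diagnosis is recorded instead; in the section's own example, "only the diagnosis (chronic kidney disease) needs to be recorded on the AE eCRF". The section then closes with the rule at issue: "Separate instances of the same clinically significant laboratory, vital sign, or ECG abnormality across visits should not be recorded as separate AEs or SAEs". It makes no exception for an abnormality that has resolved and returned, or for one that returns after study drug has stopped.

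Protocol 7.2.1 sets the recording period: "AEs and SAEs will be recorded from the first study drug administration through the follow-up visit". The 5-week post-drug period is therefore inside it.

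On the analysis side, SAP 6.9.4.7 summarises post-drug AEs separately as part of the physical-dependence assessment, by week and by sex. The note to SAP Table 14.3.1.2.1.1 gives the entry rule: "Table includes AEs with an onset after last dose of study drug". The weekly versions apply the same rule to windows of 1-7, 8-14, 15-21, 22-28 and 29-35 days after the last dose.

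**The concern.** The recording rule and the table rule do not fit together. The tables can only find an event through an onset date after the last dose. For a repeat of an abnormality already recorded on drug, the recording rule prevents any such date from being created.

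Whether serlopitant produces physical dependence is a stated safety objective. Protocol 6.2.7 schedules vital signs at every post-drug visit, and an ECG and laboratory tests at 5 weeks, for that assessment. It also has AEs reported in the period medically reviewed for signs of withdrawal. A recurrence with no new record is missing from the post-drug counts, and no event reported in that period brings it to the medical review.

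**Working it through.** There is no stated figure to reproduce and no formula applies. The check follows one event through the rules.

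**Worked case (constructed for illustration).** A clinically significant vital sign abnormality is recorded as an AE at the Week 4 visit. It is normal at Weeks 6 and 10. It is seen again at the post-drug visit 14 days after Week 10. Assume the last dose was taken on the day of the Week 10 visit.

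| Step | Under 7.1.3 as written | If the recurrence had its own record |
|---|---|---|
| AE records | 1, onset at Week 4 | 2, onsets at Week 4 and 14 days after last dose |
| Subjects with this event, treatment-emergent AE table | 1 | 1 |
| Subjects with this event, overall post-drug AE table | 0 | 1 |
| Subjects with this event, 8-14 day post-drug table | 0 | 1 |

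Reopening the old record instead of starting a new one changes nothing, because its onset stays on drug.

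**What the rule does not touch.**
- An abnormality that first appears after the last dose gets its own record and onset, and is counted.
- Symptoms, physical examination findings and confirmed diagnoses are outside the sentence.
- A finding held only as medical history from before the first dose has no earlier AE record, so a post-drug instance could be entered as a first AE.

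**What else would show the recurrence.**
- *ECG.* Table 14.3.1.5.2.3 cross-tabulates the on-drug baseline against the 5-week visit and has a clinically significant category. Table 14.3.1.5.2.1 gives threshold counts. Both are for subjects who consented to Protocol Version 3.0. Table 14.3.1.5.1.3 gives a similar shift from the pre-treatment baseline, through follow-up, for the whole Safety population.
- *Laboratory.* SAP 6.9.3 summarises out-of-range values and tabulates shifts (most reproductive hormones excepted), and the tables include follow-up visits. The comparison is with the pre-treatment baseline. Listing 16.2.8.2.1 carries the investigator's significance flag by visit.
- *Vital signs.* Table 14.3.1.6.3 gives n, mean, SD, median and range against the on-drug baseline, with no count of abnormal subjects. Listing 16.2.8.4 shows the result and its units, with no significance flag.

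**Opportunity to observe the pattern.** On drug, resolved, and returned needs at least three readings in order.
- Vital signs: Weeks 2, 4, 6 and 10, then six post-drug visits.
- ECG: Weeks 2, 4 and 10, then one post-drug reading.
- Hematology and chemistry: Weeks 2 and 10, then one post-drug draw.
- Endocrine tests: one scheduled on-drug draw (Week 10) and one post-drug draw, so scheduled samples alone cannot show the pattern.

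Vital signs therefore offer the most chances for the pattern to occur and have the least cover outside the AE records.

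**The case against.** The best defence is that the sentence was meant to stop sites re-entering one persisting abnormality at every visit, that three things must coincide before anything is lost, and that the raw values are all kept and summarised elsewhere. The dependence objective also rests on HADS and ESS, which the rule does not affect. The Protocol reports no clinically relevant changes in chemistry, hematology, vital signs or ECG in TCP-102, the Phase 2 study in prurigo nodularis, so few such events should be expected. Most of this stands, and it is why the point is minor. It does not close the gap for vital signs, and a site can only follow the words it is given, which cover separate instances without qualification.

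A reader might infer more than the documents support:

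- *That 7.1.3 contradicts 7.2.1.* Section 7.2.1 says "Any AE occurrence during the study must be recorded on source documentation and eCRF at the site", but the same sentence makes this subject to the Protocol's own instructions. It defers to 7.1.3.
- *That 7.1.3 contradicts 7.2.3.* The text there, "If an adverse event changes in severity during the same study period (e.g., treatment period), only the highest severity grade will be recorded", concerns grade changes within one AE. It says nothing about recurrence.
- *That a later serious instance could go unreported.* Under 7.4 the sponsor "must be notified within 24 hours of an AE when the investigator determines that an AE meets the protocol definition of an SAE". The trigger is the investigator's determination and needs no new AE record. Section 7.2.2 also requires a seriousness assessment for each AE and an SAE form where it is serious. Telling sites not to enter a repeat as a separate SAE does not stop an existing AE from becoming serious.

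**Conclusion.** The point holds in a narrow form. For a clinically significant laboratory, vital sign or ECG abnormality that was recorded as an AE on drug, resolved, and recurred after the last dose, the post-drug AE tables count 0 where a separate record would count 1. This follows from the wording of 7.1.3 and the table notes. It rests on sites applying 7.1.3 literally.

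The number of subjects affected cannot be derived: the documents give neither the rate of such on-drug AEs nor the rate of recurrence, so any count would be assumption. For scale only, with the planned 140 per group, each missed subject is 1/140 = 0.7% of an arm. The practical loss is mainly in vital signs. The severity is minor.

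**What to change.** Replace the last sentence of Protocol 7.1.3 with wording to this effect: a clinically significant laboratory, vital sign or ECG abnormality that persists across visits without resolution is one AE; one that recurs after documented resolution is a new AE with its own onset date. Put the same line in the eCRF completion instructions. The SAP needs no change, because its existing onset rule will then count the recurrence in the right post-drug window.

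The cost is one sentence and a few more AE records. Subject incidence by system organ class and preferred term in the treatment-emergent tables would not move, since each subject is counted once per term. Event counts would rise slightly, and a subject's maximum severity or relationship could change if the recurrence is rated higher than the first instance.
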